Aim 2: To determine how slightly-thick and mildly-thick liquids flow and whether they reduce aspiration compared to thin liquids in patients with base of tongue cancer. We will collect concurrent videofluoroscopic x-rays of swallowing and physiological measures of tongue pressure in patients with head and neck cancer using thin, slightly- and mildly-thick liquid barium stimuli. This appointment will occur approximately 3-6 months after the completion of the participants' radiation schedule. Significance: This will demonstrate the impact of consistency on bolus flow through the mouth and pharynx, controlling for the forces used to initiate flow and propel the bolus. Additionally, the data collected will aid in characterizing swallow physiology after completion of radiation therapy.

Aim 3: To determine whether the use of starch vs. gum thickeners impact the results of aims 1 and 2
The thickened liquids used for aims 1 and 2 will be prepared using both starch- and gum-based thickeners. Additionally, we will collect measures of salivary flow to control for possible interactions between thickener type and oral dryness on the results. Significance: Individuals may find one thickener more palatable or comfortable to swallow. Understanding this may impact compliance, swallowing safety and quality of life.

3. Methods

Participants:

The protocol will involve a single sample of adults, aged 18 or older with an initial cancer diagnosis of base of tongue cancer (T1-T3, N0-N2c, HPV + or -). The eligibility criteria will include completion of bilateral radiation therapy to the neck 3 months prior to enrollment, and removal of enteral feeding tube.

Participants will be asked to attend appointments and complete all data collection sessions described in this protocol. Participation involves two appointments, and two follow-up phone calls.

Exclusion Criteria:

- Participants will be accepted into the study provided they have no previous health condition known to cause swallowing impairment (e.g., stroke; brain injury; neurodegenerative disease).
- Individuals with a previous history of radiation to the head and/or neck area (prior to the current radiation treatment) will be excluded from this study given the possibility of long-term radiation effects to the swallowing apparatus.
- Individuals with a previous cancer diagnosis will be excluded from the study.

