- Participants who do not show impaired swallowing safety on thin liquids in the videofluoroscopy (Penetration Aspiration Scale scores of 1 and 2) will be withdrawn from the study.
- Participants who have had, or have a planned neck dissection will be excluded.
- Individuals with tracheostomy *in situ* will be excluded from the study.
- Individuals with cognitive communication difficulties that preclude the understanding of the protocol or following study instructions will be excluded from the study.
- Due to the requirement to swallow stimuli containing starch based thickeners, which carry a significant carbohydrate load, individuals with Type 1 Diabetes will be excluded.
- Individuals with known allergies to latex, dental glue or barium will be excluded, due to the probability that these items will come into contact with the oral mucosa during data collection.
- Children and pregnant women will be excluded from the study due to the use of radiation
- Occupational exposure to radiation exceeding half the limit specified for Ontario exposed workers within the past 12 months.

These exclusion criteria will be confirmed using a self-report questionnaire form at the time of intake into the study (see standard operating procedures [SOP], provided as an additional study document). Any questions will be clarified through discussion with the research assistant responsible for participant intake, and, where necessary with the principal investigator.

Recruitment:

This is a preliminary study that will demonstrate feasibility for a future planned extension. We propose to recruit 10-12 participants. Potential participants will be identified by study Co-PIs [name] and [name] through the current radiation therapy clinics and base of tongue cancer caseloads at Princess Margaret Cancer Centre.

Stimuli:

An array of barium and non-barium stimuli has been developed for this study. These stimuli include thin, slightly-thick and mildly-thick liquids, defined using the International Dysphagia Diet Standardisation Initiative (IDDSI) gravity flow measures. The barium stimuli used for videofluoroscopy will be prepared using E-Z-Paque® barium in 20% w/v barium concentration with starch and gum-based thickening agents (Nestlé Resource® ThickenUp® and ThickenUp Clear®). The non-barium stimuli will be prepared using Nestle's Lemon Splash® lemon-flavoured water and the same starch and gum-based thickening agents

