- j) Responses to follow-up phone calls exploring acceptance of thickened liquids.

Data Collection Procedures: Data Collection Session 1: The participant will arrive at the lab and will be asked to complete two questionnaires: the MD Anderson Dysphagia Inventory (MDADI), the Performance Status Scale for Head and Neck Cancer (PSS-HN) and the University of Washington Quality of Life Revised Version 4 (UW-WOL-R4).

Prior to data collection, saliva flow will be collected using the Saxon Test, for which the participant will chew on folded sterile gauze for 2 minutes. The gauze will be weighed before and after chewing to determine amount of saliva production. The participant will then be asked to swallow 6 non-barium

stimuli, and 2 barium stimuli thickened using starch and xanthan-gum based thickeners. After the participant has sampled each stimulus, they will be asked to rate palatability on a visual, hedonic scale (see study instruments provided).

Data Collection Session 2: Prior to data collection, saliva flow will be collected using the Saxon Test, for which the participant will chew on folded sterile gauze for 2 minutes. The gauze will be weighed before and after chewing to determine amount of saliva production. The participant will then be seated in the videofluoroscopy suite for tongue pressure sensor attachment. A silicon strip housing three 8 mm diameter pressure bulbs will be attached in midline to the roof of the participant's mouth, with the front sensor located immediately behind the participant's upper incisor teeth. The sensor strip will be attached using a medical adhesive (Stomahesive®, Convatec, St-Laurent, Quebec, Canada).

Following sensor attachment, the video output line from the fluoroscopy unit and the tongue pressure sensors will then be connected to the KayPENTAX Digital Swallowing Workstation Swallowing Signals Lab equipment, which is located on a properly insulated cart with an uninterrupted power supply and isolation transformer (see Image 1). If the participant is unable to tolerate the attachment of the sensors due to mucositis or general discomfort, we will measure tongue strength using the Iowa Oral Performance Instrument (IOPI) and collect the videofluoroscopy measures without the use of the adhered sensors.

Image 1. Tongue pressure sensors.

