Participants will be asked to swallow a series of thin, slightly-thick and mildly-thick barium stimuli 1 (3 boluses each of 5 stimuli, for a total of 15 boluses) in videofluoroscopy, with concurrent measurement of tongue-palate pressure. Videofluoroscopy will be performed at optimal temporal resolution (30 pulses/second) and captured at 30 frames/second. The stimuli will be presented in a randomized design, blocked by stimulus type. Participants will be allowed to take natural sized sips of each stimulus from cups containing 40 ml. Sip volume and mass will be calculated, by weighing the cups prior to and after the videofluoroscopic assessment.

Data Processing:

The tongue-pressure waveform will be segmented using an automatic segmentation algorithm developed previously in the PI's lab. Similarly, the videofluoroscopy recordings will be spliced into single bolus clips and the audio channel will be muted to remove cues that might bias rating. Blinded videofluoroscopy rating will then be performed in duplicate by trained raters in the [name] Lab following established procedures (see SOP provided as an additional study document). Discrepancies between raters will be flagged and resolved at consensus meetings, as required. These procedures will yield a

large number of parameters for each swallow. We will use established measures within our lab to collect and analyze measures related to kinematics and residue.

[figure not shown]
Follow-up phone calls: If deemed appropriate, the participant may be offered the opportunity to complete a follow-up component. For those willing to participate, this optional experiment will involve two follow-up telephone calls (at 2 weeks and 3 months following the videofluoroscopy) to determine compliance with use of thickened liquids recommended following the videofluoroscopy (see study instruments provided for questionnaires).

Data Analysis:

For Aim 1, we will compare hedonic ratings for the different stimuli using a univariate ANOVA. It is hypothesized that ratings will be significantly better for the thin and slightly thick stimuli compared to the mildly-thick stimuli, and that a preference will be seen for the gum compared to the starch thickened liquids.

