For Aim 2, blinded videofluoroscopy rating will be performed in duplicate, and discrepancies between raters will be flagged and resolved at a consensus meeting. The frequency of aspiration will be explored with the thin stimuli and compared to the prevalence of aspiration when thickeners are introduced using chi-square statistics.

We will model the impact of stimulus on two timing measures of pharyngeal bolus flow from the videofluoroscopy (i.e., a) the interval from the bolus passing the mandibular ramus until laryngeal vestibular closure; b) the interval from the bolus passing the mandibular ramus until entering the upper esophageal sphincter) and on measures of post-swallow residue (Normalized Residue Ratio Scale). The Saxon test results regarding oral dryness will be used as a covariate for all analyses, as illustrated in the Figure below:

A path analysis approach will be used to first identify differences in tongue pressure across stimuli

(Question 1). If confirmed, this potential modulator will be added to the Question 2 model as a covariate (Question 3). The planned analyses will involve linear mixed model repeated measures ANOVAs with a factor of stimulus.

For Aim 3, we will use qualitative methods to describe participant reports of adherence to the prescribed thickener. Information from the quality of life and performance status scales collected in session 1 will be used to inform our understanding of variations on patterns of thickener acceptance.

4. Risks and Benefits

Risks

The following risks will be disclosed to all participants prior to obtaining their consent to participate:

- a) Participants may experience local mucosal irritation from the glue on the adhesive strip used to attach the tongue-pressure bulbs for data collection. The glue usually wears off within 90 minutes following the conclusion of data collection. In the incidence that participants are unable to tolerate the attachment of the sensors, we will use the IOPI tongue bulbs to collect tongue measurements, and collect videofluoroscopic data using the same protocol.
- b) Participants may dislike the taste or texture of some of the thickened liquid stimuli in the study. Participants will be reminded that they are free to discontinue participation at any time.

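### Aim 1 names no within-participant model for eight ratings per person; treating them as independent would mainly cost power, and could inflate false positives for gum versus starch only

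*Combined protocol and SAP*

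**What the plan says.** Recruitment (section 3): "We propose to recruit 10-12 participants". They form a single sample with no parallel groups.

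Data Collection Session 1 (section 3): each person tastes six products without barium, plus "2 barium stimuli thickened using starch and xanthan-gum based thickeners". Every product tasted is scored by the same person, as the session description makes clear: "After the participant has sampled each stimulus, they will be asked to rate palatability on a visual, hedonic scale". That makes 6 + 2 = 8 ratings per person, or 80 to 96 in all if complete. The six non-barium stimuli are not listed.

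Data Analysis, Aim 1: "we will compare hedonic ratings for the different stimuli using a univariate ANOVA". Two hypotheses follow. The first concerns thickness: "ratings will be significantly better for the thin and slightly thick stimuli compared to the mildly-thick stimuli". The second concerns thickener type, where the protocol predicts this: "a preference will be seen for the gum compared to the starch thickened liquids".

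Data Analysis, Aim 2: after the timing, residue and tongue-pressure models, and before Aim 3, comes the sentence "The planned analyses will involve linear mixed model repeated measures ANOVAs with a factor of stimulus". The same text makes the Saxon test result a covariate for all analyses.

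Purpose and Specific Aims, Aim 3: "Individuals may find one thickener more palatable or comfortable to swallow". This section also expects a possible interaction between thickener type and oral dryness.

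**The concern.** The eight ratings come from the same mouth in the same session, so they are repeated measures. The Aim 1 sentence names no participant, random or repeated factor, while the Aim 2 text does use repeated-measures language. Read plainly, Aim 1 is a one-way ANOVA that takes 80 to 96 ratings as independent.

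Two things could then go wrong. A shared tendency to rate high or low is left in the error term, which makes it too large and hides real differences. Alternatively, if people differ in which thickener they like, several ratings per thickener from one person are partly redundant. The error term is then too small for the gum-versus-starch comparison. A participant term removes the first problem but not the second, because it assumes that all pairs of stimuli correlate equally.

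Aim 1 hypothesises a significant difference, so tests are intended even though this is a pilot. With 10-12 people, within-person comparison is the main source of precision.

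**Working it through.** **Nothing to reproduce.** The sample size is stated without alpha, power, effect size, SD or correlation.

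**Assumptions (not in the documents).** Normal ratings with total variance 1; two-sided 5% level; n = 12 unless stated. Stimuli: two thin, slightly thick starch and gum, mildly thick starch and gum, and two barium (one starch, one gum). Gum versus starch uses the four non-barium thickened stimuli (2 v 2). Correlation is *w* within a thickener group and *a* across groups. The groups are thin (2 stimuli), starch (3) and gum (3), with one barium stimulus in each of the last two. Error rates and power are simulated.

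**Gum versus starch: formulas.**
- True variance of one person's score (mean gum minus mean starch): 1 + *w* − 2*a*.
- Variance if ratings are taken as independent: 1/2 + 1/2 = 1.
- Expected participant-adjusted error: 1 minus the mean correlation over the 28 stimulus pairs, 7 of which are within a group (1 + 3 + 3).
- The independent test is therefore conservative when *w* < 2*a* and liberal when *w* > 2*a*.

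**Case 1, equal correlation (*w* = *a* = 0.5).** The true variance is 1 + 0.5 − 1.0 = 0.5, so the independent analysis uses twice the right value. For an assumed 0.5 SD effect, the standard error is √(0.5/12) = 0.204 (ratio 2.45), but the independent test uses √(1/12) = 0.289 (ratio 1.73).

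| Equal correlation 0.5 | Independent | Participant term | Per-person score |
|---|---|---|---|
| Power, n = 12 | 38% | 68% | 61% |
| Power, n = 10 | 30% | 60% | 51% |
| Type I error, n = 12 | 0.9% | 5.0% | 5.0% |

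**Case 2, thickener preference varies (*w* = 0.5, *a* = 0.2).** The true variance is 1 + 0.5 − 0.4 = 1.1, so the independent error is slightly too small. The mean pair correlation is (7 × 0.5 + 21 × 0.2)/28 = 0.275, so the participant-adjusted error is 0.725. The true variance is 1.1/0.725 = 1.52 times that. The gap *w* − *a* = 0.3 means a between-person SD of √(2 × 0.3) = 0.77 in gum-minus-starch liking.

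| Type I error, gum v starch, n = 12 | Independent | Participant term | Per-person score |
|---|---|---|---|
| 0.5 within, 0.4 across | 2% | 7% | 5% |
| 0.5 within, 0.2 across | 6% | 11% | 5% |
| 0.7 within, 0.1 across | 11% | 16% | 5% |

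The last row needs a between-person SD of √(2 × 0.6) = 1.10, larger than the SD of a single rating, so it is an extreme case.

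**Case 3, thin and slightly thick versus mildly thick, same thickener grouping.** The contrast is five stimuli against three, with one barium stimulus on each side.

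| Type I error, consistency, n = 12 | Independent | Participant term | Per-person score |
|---|---|---|---|
| 0.5 within, 0.4 across | 1.2% | 5.1% | 5.1% |
| 0.5 within, 0.2 across | 2.2% | 5.0% | 5.0% |
| 0.7 within, 0.1 across | 2.5% | 5.0% | 5.0% |

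Each thickener appears on both sides of this contrast, so a personal preference for one thickener largely cancels. The independent test stays conservative and a participant term is enough.

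**The case against.** **The model may only be unstated.** *Univariate* can mean one outcome with participant in the model, and the mixed-model sentence names no aim. A reader might infer that the plan commits to an independent-ratings analysis. The documents do not prove that; they leave the model open. This softens the charge but not the remedy, since the Aim 1 sentence needs completing either way.

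**False positives for both hypotheses.** A reader might infer that the thickness comparison is also at risk of inflation. It would be if ratings correlated more within thickness groups than across them: at 0.5 within and 0.2 across such groups, type I error is about 13% independent and 21% with a participant term. No section gives a reason for that pattern. Aim 3 speaks only of thickener type, and under that grouping the thickness test is conservative. This objection stands, and those figures are not part of the point.

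**The two directions are not equally likely.** This also stands. A mild preference split (0.5/0.4) leaves the independent test conservative, so lost power is the main expected harm.

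**It is a feasibility pilot, and the stimulus list may be in the instruments or procedures it refers to.** Fair, and it limits the seriousness. The protocol still states hypotheses to be tested, and the stimulus list would not supply the missing participant term.

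**Conclusion.** The point holds as an incompletely specified analysis whose plain reading gives a wrong error term. Under equal correlation of 0.5, n = 12 and a 0.5 SD effect, ignoring participant cuts gum-versus-starch power from 68% (participant term) or 61% (per-person score) to about 38%, with type I error near 1%. Inflation is a secondary risk, confined on the documents' own rationale to gum versus starch: about 6% independent and 11% with a participant term only, at 0.5/0.2.

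It would go too far to say that a participant term is inadequate for both hypotheses; for the thickness contrast it holds 5%. Every figure depends on the assumed correlations, effect and stimulus set. Confidence is medium. The change should be made, but it does not threaten the study.

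**What to change.** Replace the Aim 1 method with a named within-participant analysis. This can be per-participant contrast scores, or a mixed model or repeated-measures ANOVA with participant as a random effect plus a sphericity correction or a participant-by-thickener term. Specifically:

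- **Gum versus starch:** one score per participant, mean gum minus mean starch among thickened stimuli only, tested against zero.
- **Thickness:** thin minus mildly thick and slightly thick minus mildly thick as two separate within-participant contrasts. If thin and slightly thick are pooled, thin alone could carry the result.
- **Saxon covariate:** keep it, for example by regressing each score on centred Saxon and testing the intercept. A main effect of Saxon cancels from a within-person score, so the slope addresses the dryness-by-stimulus interaction that Aim 3 anticipates.
- **Ordinal scale:** if the hedonic scale is ordinal, add a signed-rank test as a sensitivity analysis.
- **Barium:** state the thickness and thickener of the two barium stimuli and whether they enter each contrast.

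The cost is one or two sentences and no new data. If correlations are in fact equal, per-person scores give up some power (61% against 68%; signed-rank 56%). The Saxon term costs one degree of freedom (11 to 10 with n = 12). A Greenhouse-Geisser-corrected overall test is conservative here, at about 2% type I error with eight stimuli, 12 people and equal correlation of 0.5, so the named contrasts should carry the inference.

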Dysphagia (swallowing impairment) involves two primary concerns: 1) the ability to swallow safely, without material entering the airway; 2) the ability to swallow efficiently, without leaving residue behind in the pockets of the pharynx. Impaired swallowing safety is linked to pneumonia while impaired efficiency contributes to risk of malnutrition. Dysphagia is common in patients with head and neck cancer prior to, and as a result of treatment. Radiation treatment for the cancer can cause and exacerbate symptoms of dysphagia. Due to an increase in the prevalence of oropharyngeal cancers secondary to the Human Papilloma Virus (HPV), a growing number of individuals are receiving radiation treatment for their disease. However, because of the typically young age at diagnosis, these individuals can expect longer post-treatment lifespans during which there is a significant chance for negative sequelae to develop, including dysphagia. When a person presents with dysphagia, a common intervention is to alter the consistency of the foods and fluids they consume. However, we lack evidence to guide the modification of food and liquid textures for clinical benefit. In particular, we lack studies demonstrating the effect of texture modification as an intervention in the head and neck cancer population. In this study, we propose to measure the flow of thin, slightly thick and mildly thick liquids in patients who have completed radiation treatment for base of tongue cancer, to understand whether or not thickened liquids provide benefit.

We have three specific aims:

Aim 1: To determine whether slightly-thick and mildly-thick liquids are palatable and acceptable to patients with base of tongue cancer. We will collect palatability measures for starch- and gum-thickened liquids with slightly-thick and mildly-thick consistencies, as defined by the International Dysphagia Diet Standardisation Initiative syringe flow test. We will also collect baseline quality of life measures to understand the impact of swallowing impairment on the participant's quality of life. Following a videofluoroscopy swallowing assessment (described under Aim 2), participants will be advised to use thickened liquids that are effective for improving their swallowing. A follow-up phone call will monitor compliance and acceptance of this recommendation. Significance: This will determine how likely participants are to adhere to a thickener recommended based on its efficacy to reduce aspiration.

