- c) Participants may experience some fatigue during the videofluoroscopy data collection session. Participants will be reminded that they should disclose any fatigue or discomfort to the research team, and that they are free to discontinue any particular session or to withdraw from the study at any time.
- d) Participants will receive additional exposure to radiation during the videofluoroscopy, in addition to their recent radiation treatment protocol. Based on a previous videofluoroscopic study that we have conducted in healthy adults, the study is expected to involve 118+/-18 seconds of radiation exposure (Molfenter & [name], 2013), with an associated dose estimate of <0.35 milliSieverts. Moro and Cazzani showed that this dose (0.35mSv) corresponds to a risk of 1 in 39,000 of developing a radiation-induced stochastic effect from a videofluoroscopy. We will use a 2-minute warning bell to alert the data collection team to exposure time, and will terminate the protocol at the first opportunity following the bell.
- e) Aspiration (entry of material into the airway) is a possible risk during the videofluoroscopic swallowing study that will be performed. This risk is always present for videofluoroscopic swallowing studies, which are intended to document the presence and severity of swallowing abnormalities, including (but not limited to aspiration). When aspiration is observed, standard procedures will be followed to encourage coughing and throat clearing to expel the aspirated material. The protocol will be terminated immediately. Any participant who experiences aspiration will be counseled regarding aspiration prevention strategies and aspiration-risk following the videofluoroscopy.
- f) Choking is an extremely unlikely event. However, in the event of choking, routine emergency procedures will be followed. All study personnel carry current CPR certification.

g) In the unlikely event that an incidental finding is noted on the videofluoroscopy (such as a diverticulum or a mass) the attending SRRL licensed speech-language pathologist will consult the on-call radiologist and generate a clinical report documenting the observation. These findings will be communicated with the participant as per usual clinical practice and follow up with their physician will be recommended.

Benefits

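### Participants are retained on a Penetration Aspiration Scale threshold, but Aim 2 compares undefined aspiration, so some retained participants may be unable to show a reduction and others may have their session stopped

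*Combined protocol and SAP*

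**What the plan says.** Three parts of the protocol bear on the same outcome.

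- **Retention (section 3, Exclusion Criteria).** Participants who "do not show impaired swallowing safety on thin liquids in the videofluoroscopy (Penetration Aspiration Scale scores of 1 and 2") are withdrawn. By complement, those scoring above 2 on thin liquid stay.
- **Outcome (section 2, Aim 2; section 3, Data Analysis).** Aim 2 asks of the thickened liquids "whether they reduce aspiration compared to thin liquids in patients with base of tongue cancer". The analysis is "The frequency of aspiration will be explored with the thin stimuli and compared to the prevalence of aspiration when thickeners are introduced", by chi-square. No PAS score is given for aspiration, and no analysis of PAS or of penetration is planned. Aim 2 has other outcomes as well: "We will model the impact of stimulus on two timing measures of pharyngeal bolus flow from the videofluoroscopy", together with post-swallow residue.
- **Termination (section 4, Risks, item e).** When aspiration is observed, "The protocol will be terminated immediately".

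The only gloss on the term is in that same risk item: "Aspiration (entry of material into the airway) is a possible risk". Section 2 describes safe swallowing in similar words: "the ability to swallow safely, without material entering the airway".

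Section 3 plans three boluses of each of five stimuli, 15 in all, in randomised order blocked by stimulus. Under Benefits, section 4 expects some participants who aspirate to go on to swallow more safely on thickened stimuli in the examination.

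**The concern.** The scale used for retention grades, by its name, both penetration and aspiration. The outcome names only aspiration. The sample is therefore selected on one construct and the safety question is tested on another that is left undefined and may be narrower.

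If it is narrower, part of the retained sample can only stay level or get worse in the safety comparison. If it is not, the qualifying event and the terminating event coincide. In either case a null or incomplete safety result could reflect how the outcome and the session rules fit together rather than how thickeners perform. That matters for a pilot meant to inform a planned extension.

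**Working it through.** **The plan's own figures.** 3 × 5 = 15 boluses is correct. The recruitment target of 10-12 cannot be reproduced, because no alpha, power, event rate or effect size is given.

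**The two readings of aspiration.**

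| Reading | Retained for penetration only | Seen to aspirate on thin |
|---|---|---|
| Aspiration excludes penetration | Zero events on thin; can only stay level or worsen | Informative, but the session stops when aspiration is seen |
| Aspiration includes penetration (risk-section gloss) | Counts as an event; if seen live, the session stops | Same |

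On both readings, every stimulus block scheduled after the observed event is lost.

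**Size under the narrow reading.** Let q be the share of retained participants who penetrate but do not aspirate on thin. The documents give no q, so 0, 25, 50 and 75% are assumed. With n retained, a = n(1 − q) participants can improve, and the largest observable risk reduction is a/n. In the best case every one of them stops aspirating on thickened liquid. Exact McNemar then gives p = 2 × 0.5^a, and the uncorrected chi-square compares a/n with 0/n. The last column gives exact McNemar power if an assumed 60% of the a participants become safe. Two-sided 0.05 is assumed throughout, and truncation is ignored.

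| n = 12, q | a | Largest reduction | Best-case McNemar p | Best-case chi-square p | Power at 60% |
|---|---|---|---|---|---|
| 0% | 12 | 1.00 | 0.0005 | <0.001 | 84% |
| 25% | 9 | 0.75 | 0.004 | 0.0001 | 48% |
| 50% | 6 | 0.50 | 0.031 | 0.005 | 5% |
| 75% | 3 | 0.25 | 0.25 | 0.064 | 0% |

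A participant-level sign test needs at least 6 changes in one direction: 2 × 0.5^5 = 0.0625 and 2 × 0.5^6 = 0.031. If 25, 50 or 75% of retained participants aspirate on thin, the binomial chance that fewer than 6 can improve is:

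- n = 10: 98%, 62%, 8%
- n = 11: 97%, 50%, 3%
- n = 12: 95%, 39%, 1%

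**What selection on thin does.** Suppose thickening has no effect, each bolus independently has probability r of PAS above 2, and a participant is retained if any of the three thin boluses exceeds 2. The probability of retention is 1 − (1 − r)^3. Among those retained, the per-bolus rate on thin is r / [1 − (1 − r)^3], while on a thickened stimulus it stays r.

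At r = 0.2: 1 − 0.8^3 = 0.488, and 0.2 / 0.488 = 0.41 on thin against 0.20 on thickened.

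At participant level (any of three boluses above 2), every retained participant is a case on thin. Each is a non-case on a given thickened stimulus with probability (1 − r)^3. With n = 11, the chance of 6 or more one-directional changes with no true effect is:

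| r | (1 − r)^3 | P(6 or more of 11) |
|---|---|---|
| 0.1 | 0.729 | 0.95 |
| 0.2 | 0.512 | 0.53 |
| 0.3 | 0.343 | 0.14 |
| 0.5 | 0.125 | 0.001 |

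The planned aspiration comparison has the same problem. If an aspirated bolus always scores above 2, a thin bolus with aspiration guarantees retention. The per-bolus aspiration rate on thin is then divided by the same 1 − (1 − r)^3. At r = 0.2 both outcomes are inflated on thin by 1 / 0.488 = 2.05.

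**The case against.** The strongest reply is that aspiration may not be narrow. The risk-section gloss and the section 2 description of safe swallowing are close in wording, so aspiration could mean the same as the impaired safety used for retention. That stands as a possible reading, and it removes the mismatch. It does not rescue the comparison, because the qualifying swallow would then trigger termination when seen live.

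A reader might infer that penetration-only participants cannot show any benefit of thickening. The documents do not support that: the timing intervals and residue are also Aim 2 outcomes, and these participants can change on them.

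A reader might also infer that anyone who completes all 15 boluses has shown no aspiration. That does not follow. Aspiration could occur on the last bolus, or be found only at the later blinded rating. The rule removes only what is seen live before the end.

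Three further points stand. The plan names chi-square, not a sign test, and the best-case chi-square is still 0.005 at n = 12 with half the sample penetration-only; the sign test and McNemar figures are participant-level benchmarks. This is a feasibility pilot that describes the comparison as exploratory, so missing p < 0.05 carries limited weight. And replacing aspiration with PAS above 2 on the same thin boluses would be unsafe by itself, as the selection calculation shows.

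**Conclusion.** The concern holds for the airway-safety comparison only. Retention and outcome are not tied to the same stated PAS threshold. Under the narrow reading the observable reduction is capped at the share of retained participants who aspirate on thin; under the broad reading retention and termination collide. On both, a participant seen to aspirate loses later stimuli, which conflicts with the 15-bolus comparison and with the Benefits text.

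The cap follows from logic and applies to any test. The percentages rest on assumed shares, an assumed 60% conversion and an assumed 10-12 retained. Since 10-12 is the number recruited and PAS withdrawals come out of it, the retained number may be smaller. The selection figures assume independent boluses with a common risk and retention on any thin bolus above 2; they show direction and possible size, not an estimate for this trial.

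This should be corrected before analysis, but in a pilot it is not a fatal flaw.

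**What to change.** 1. **Define the outcome and add a second one.** Keep aspiration as the Aim 2 question and state which PAS scores count as aspiration. Add a within-participant, bolus-level comparison of PAS by stimulus, either above 2 versus 1-2 or ordinal. Confirm in the text that PAS is rated on every bolus. Section 3 describes duplicate blinded rating but names only kinematics and residue among the measures, so per-bolus PAS rating is inferred, not stated.

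2. **Handle selection for both outcomes.** Either run the thin-versus-thickened comparison in all participants examined, before PAS withdrawal is applied, or use separate thin boluses for selection and for analysis. If neither is possible, state that regression to the mean favours the thickened stimuli. The first option needs thickened-stimulus data from those later withdrawn, so the protocol should say when the withdrawal rule is applied. The second leaves fewer thin boluses for the comparison if the total stays at 15.

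3. **Reconcile the termination rule** in section 4 (Risks, item e) with the 15-bolus procedure and Aim 2 analysis in section 3 and with the Benefits text in section 4. How that rule should read is for the clinical team. Changing the outcome does not restore boluses lost to termination.

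**Cost.** Item 1 is mainly wording and a small amount of extra analysis, provided PAS is already rated per bolus. The downside is a broader outcome reported beside aspiration. Item 2 may touch the examination procedure, so it is more than an analysis edit.
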